### **Model Checking & Diagnostics**

- The Kenward-Roger (KR) method (Kenward, 1997) for approximating the denominator degrees of freedom and correcting for bias in the estimated variance-covariance of the fixed effects will be used in the analyses. This will be achieved by specifying the DDFM=KR option in the MODEL statement within PROC MIXED.
- Appropriate graphs will be reviewed as part of the model checking process to ensure that
  distributional assumptions hold. These will include a normal probability plot of the residuals
  and a plot of the residuals versus the fitted values (checking the normality assumption and
  constant variance assumption of the model, respectively).

#### **Model Results Presentation**

 The adjusted mean change from baseline with corresponding standard error for each treatment group will be presented. The estimated treatment difference will be presented together with 95% confidence interval (CI) for the difference and p-value for the inequality comparison.

For the co-primary endpoints and the secondary endpoints for the EOS visit/time-period only, a forest plot will be produced to present the estimated treatment differences and 95% CIs.

# 4.4. Other Endpoints Analyses

### 4.4.1. Definition of endpoints

The other endpoints are:

- Change from baseline in mean overall symptom (VAS) score from Week 49 through to Week 52
- Achieving a one point or greater decrease from baseline in NP Score at Week 52 without first having nasal surgery (actual) or disease-modulating medication for CRSwNP
- Change from baseline in mean individual symptom (VRS) score for facial pain from Week 49 through to Week 52
- Change from baseline in mean individual symptom (VRS) score for mucus in throat from Week 49 through to Week 52
- Change from baseline in the mean nasal polyps symptoms composite score (combining VRS scores for nasal obstruction, rhinorrhoea (runny nose), loss of smell, and mucus in throat) from Week 49 through to Week 52
- Change from baseline in mean CRS symptoms and facial pain composite score (combining VRS scores for nasal obstruction, rhinorrhoea (runny nose), loss of smell, and facial pain) from Week 49 through to Week 52
- Achieving a meaningful decrease from baseline in their mean individual symptoms VRS and composite VRS from Week 49 through to Week 52 without first having nasal surgery (actual) or disease-modulating medication for CRSwNP.
- Further details on meaningful decrease for each individual symptom VRS and composite VRS are described in Section 4.4.2
- Achieving an 8.9-point or greater decrease from baseline in SNOT-22 total score at Week 52 without first having nasal surgery (actual) or disease-modulating medication for CRSwNP
- Achieving a 28-point or greater decrease from baseline in SNOT-22 total score at Week 52 without first having nasal surgery (actual) or disease-modulating medication for CRSwNP
- Change from baseline in SF-36 Mental Component Summary (MCS) score, Physical Component Summary (PCS) score and eight domains at Week 52
- Change from baseline in WPAI-GH scores at Week 52

The overall visual analogue scale (VAS) symptoms score will be collected daily in the morning via the eDiary. Participants will be asked to rate their overall symptoms at their worst over the previous 24 hours. A scale from 0 (None) to 100 (As bad as you can imagine) will be used. The final VAS scores that are reported will be derived from the electronically captured score by dividing each score by 10 and will range between 0 and 10. This endpoint will be handled in the same way as the co-primary VRS endpoint, with daily data being collapsed into 4-week time periods as described in Section 6.3.4.2.

A nasal obstruction VAS score will also be collected daily in the morning via the eDiary at key time-periods during the study. The data from this endpoint will be collapsed into the expected time periods as described in Section 6.3.4.2.

The VRS composite scores will be derived for each day by taking the mean of the individual VRS scores for that day. All of the individual VRS scores contributing to a composite score must be non-missing in order to derive the mean.

All VRS endpoints will be handled in the same way as the co-primary VRS endpoint, with daily data being collapsed into 4-week time periods as described in Section 6.3.4.2.

The short-form-36 (SF-36) questionnaire consists of 36 self-administered questions that cover 8 health domains: physical functioning (PF), role physical (RP), bodily pain (BP), and general health (GH), vitality (VT), role emotional (RE), social functioning (SF), and mental health (MH) with a recall of 4 weeks. Certified scoring of the SF-36 survey will be performed using OPTUM TM software. The 8 domain scores are provided by the software. Scale scores range from 0 to 100 where higher scores indicate better quality of life.

The work productivity and activity impairment (WPAI) questionnaire is an instrument to measure impairment in paid and unpaid work and daily activities. Six questions will be collected at each visit including employment status, hours missed from work due to health problems and due to other reasons, hours actually worked, and how much health problems affected productivity and activity.

The following measures will be derived from the 6 WPAI-GH questions ranging from 0 (no impairment) to 100 (full impairment):

Derived Outcomes Derivation	Derived Outcomes Derivation	
Work time missed due to health (%)	100 * Q2 / (Q2+Q4)	
Impairment while working due to health (%)	10 * Q5	
Overall work impairment due to health (%)	100* Q2 / (Q2 + Q4) + [(1 - (Q2 / (Q2+Q4))) x	
, , ,	(Q5 / 10)]	
Activity impairment due to health (%)	10 * Q6	

Note (each question with a recall of 7 days):

- Q1 = Currently Employed
- Q2 = Time (hours) missed from work due to health problems during the past seven days
- Q3 = Time (hours) missed from work due to other reasons during the past seven days
- Q4 = Time (hours) actually worked during the past seven days
- Q5 = Productivity affected by health problems while working during the past seven days
- Q6 = Ability to do regular daily activities affected by health problems during the past seven days

Participants not currently employed will only answer Q6. Participants who answer 0 to Q4 will not answer Q5.

If any of the responses used to derive a score are missing or if a participant is not currently employed then the relevant score (work time missed, impairment while working, overall work impairment) will be set to missing.

For those who missed work and did not actually work in the past seven days, the percent overall work impairment due to health will be equal to the percent work time missed due to health.

For SF-36 and WPAI-GH, the intercurrent event of surgery and disease-modulating medication for CRSwNP will be handled under the composite strategy by assigning participants their worst observed score prior to the event. All other intercurrent events described under the primary estimand strategy in Section 1.1.2 will be handled using a treatment policy strategy.

For all responder endpoints, participants who undergo nasal surgery or initiate a disease-modulating medication for CRSwNP will be included in the analysis as non-responders for all time points following the event, whichever occurred first. For participants with missing baseline data, a responder status will not be derived. Participants with missing data at a particular post-baseline visit / timepoint will be treated as non-responders for that visit/ timepoint. All other intercurrent events described under the primary estimand strategy in Section 1.1.2 will be handled using a treatment policy strategy.

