8.9.2. Work Productivity and Activity Impairment Questionnaire (WPAI)

WPAI will be assessed by the participant at study visits described in Table 1.

The WPAI questionnaire is an instrument to measure impairments in both paid work and unpaid work [Reilly, 2002]. It measures absenteeism, presenteeism as well as the impairments in unpaid activity because of health problem during the past seven days. It has been validated to quantify work impairments for numerous diseases such as asthma, psoriasis, irritable bowel syndrome, ankylosing spondylitis and Crohn's disease [Reilly, 2004; Reilly, 2010; Reilly, 2008]. In addition, the WPAI questionnaire has been used to compare work impairments between treatment groups in clinical studies and trials or between participants with different disease severity levels [Reilly, 2004; Reilly, 2010; Reilly, 2008; Revicki, 2007; Pearce, 2006; Chen, 2008].

The WPAI-GH consists of six questions: 1 = currently employed; 2 = hours missed due to health problems; 3 = hours missed other reasons; 4 = hours actually worked; 5 = degree health affected productivity while working (using a 0 to 10 VAS); 6 = degree health affected productivity in regular unpaid activities (VAS) [Reilly, 1993]. The recall

and did not actually work in the past seven days, the percent overall work impairment due

period for the questions 2 to 6 is 7 days. Four main outcomes can be generated from the WPAI: 1) percent work time missed due to health for those who were currently employed; 2) percent impairment while working due to health for those who were currently employed and actually worked in the past seven days; 3) percent overall work impairment due to health for those who were currently employed; 4) percent activity impairment due to health for all respondents [Reilly, 2002]. For those who missed work

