### 4.4.2. Main analytical approach

Summary statistics by visit will be provided for the SF-36 and WPAI-GH endpoints.

Summary of responder status by visit will be provided for the 28-point SNOT-22 responder endpoint.

Summary statistics for change from baseline at the key time-periods when it was collected will be provided for overall VAS score.

The change from baseline endpoints related to VAS and VRS scores will be analysed in the same way as the co-primary endpoints.

For the endpoint, achieving a meaningful decrease from baseline in their mean individual symptoms VRS and composite VRS from Week 49 through to Week 52 without first having nasal surgery (actual) or disease-modulating medication for CRSwNP, the clinically meaningful VRS cut-points for mean individual symptoms VRS and composite VRS are as follows:

- Achieving a 1-point or greater decrease from baseline in nasal obstruction VRS total score at Week 52 without first having nasal surgery (actual) or disease-modulating medication for CRSwNP
- Achieving a 1-point or greater decrease from baseline in rhinorrhoea VRS total score at Week 52 without first having nasal surgery (actual) or disease-modulating medication for CRSwNP
- Achieving a 0.9-point or greater decrease from baseline in loss of smell VRS total score at Week 52 without first having nasal surgery (actual) or disease-modulating medication for CRSwNP
- Achieving a 0.8-point or greater decrease from baseline in facial pain VRS total score at Week 52 without first having nasal surgery (actual) or disease-modulating medication for CRSwNP
- Achieving a 1-point or greater decrease from baseline in mucous in throat VRS total score at Week 52 without first having nasal surgery (actual) or disease-modulating medication for CRSwNP
- Achieving a 0.8-point or greater decrease from baseline in composite nasal polyps symptoms VRS total score at Week 52 without first having nasal surgery (actual) or disease-modulating medication for CRSwNP

• Achieving a 0.8-point or greater decrease from baseline in composite CRS symptoms and facial pain VRS total score at Week 52 without first having nasal surgery (actual) or disease-modulating medication for CRSwNP

The remaining other endpoints will be analysed as described below:

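### The SAP's WPAI-GH overall work impairment formula applies the factor 100 to only one of its two terms, so at-work impairment can add at most 1 point to a 0–100 score

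*SAP*

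**What the plan says.** SAP section 4.4.1 lists "Change from baseline in WPAI-GH scores at Week 52" among the other endpoints and then gives a table of four derived outcomes. The sentence introducing the table sets their scale: "The following measures will be derived from the 6 WPAI-GH questions ranging from 0 (no impairment) to 100 (full impairment").

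The formulas in the table are:

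- Work time missed (%): 100 × Q2/(Q2+Q4).
- "Impairment while working due to health" (%): 10 × Q5.
- Overall work impairment (%): "100* Q2 / (Q2 + Q4) + [(1 - (Q2 / (Q2+Q4))) x" followed on the next line by (Q5/10) and a closing square bracket.
- Activity impairment (%): 10 × Q6.

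A participant who missed work and worked no hours in the past seven days is given the work-time-missed percentage as the overall score. After surgery or the start of a disease-modulating medication, the composite strategy for WPAI-GH works by "assigning participants their worst observed score prior to the event".

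Protocol section 8.9.2 describes the same outcome as "percent overall work impairment due to health for those who were currently employed" and gives Q5 a 0–10 response scale. It gives no formula. SAP section 4.4.2 states the planned analysis: "Summary statistics by visit will be provided for the SF-36 and WPAI-GH endpoints".

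**The concern.** The two terms of the overall score are on different scales. The absence term carries the factor 100 and runs from 0 to 100. The at-work term is a product of two fractions and runs from 0 to 1. The result cannot be the 0–100 measure that the SAP announces just above the table. It also disagrees with the row's own (%) label and with the protocol's description of the outcome as a percent.

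Overall work impairment is the WPAI-GH score that combines absence with impairment while at work. Programmed as printed, it would be almost a copy of work time missed, and a treatment effect on at-work impairment would all but vanish from it. A table of such values, labelled as percentages, would be misread. The rule for intercurrent events would inherit the problem, because the visit with the worst score could be the wrong one.

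**Working it through.** **Inputs.** Q2, Q4 and Q5 are as defined in SAP 4.4.1, and the 0–10 range of Q5 comes from protocol 8.9.2. Write m = Q2/(Q2+Q4) for the fraction of work time missed. The hours used below are illustrative; the bounds do not depend on them.

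**Printed formula:** S = 100m + (1−m)(Q5/10).

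**With 100 applied to the whole sum:** S* = 100 × [m + (1−m)(Q5/10)].

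**Step 1: can the printed formula reproduce the stated 0–100 range?** The at-work term (1−m)(Q5/10) is a product of two numbers between 0 and 1, so it is at most 1, reached when Q2 = 0 and Q5 = 10. For anyone who worked (Q4 > 0, hence m < 1), the largest possible score is 100m + (1−m) = 100 − 99(1−m), which is below 100. With no hours missed the ceiling is 1. A score of 100 arises only for those who worked no hours. The stated range is therefore not reproduced. Under S*, Q5 = 10 gives 100 × [m + (1−m)] = 100 for every m, and Q2 = 0 with Q5 = 0 gives 0, so the range is restored.

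**Step 2: worked values.**

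| Q2 | Q4 | Q5 | m | Printed S | Corrected S* |
|---|---|---|---|---|---|
| 0 | 40 | 10 | 0 | 0 + 1 × 1 = 1 | 100 |
| 4 | 36 | 10 | 0.1 | 10 + 0.9 × 1 = 10.9 | 100 |
| 20 | 20 | 10 | 0.5 | 50 + 0.5 × 1 = 50.5 | 100 |
| 8 | 32 | 6 | 0.2 | 20 + 0.8 × 0.6 = 20.48 | 68 |
| 8 | 32 | 3 | 0.2 | 20 + 0.8 × 0.3 = 20.24 | 44 |

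In the first row the separate at-work score, 10 × Q5, is 100 for the same answers.

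**Step 3: effect on a change score.** From the last two rows, halving Q5 from 6 to 3 at constant hours gives 20.24 − 20.48 = −0.24 as printed and 44 − 68 = −24 when corrected. In general a one-unit change in Q5 moves S by (1−m)/10 and S* by 10(1−m), a 100-fold difference. The separate at-work score moves properly, from 60 to 30.

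**Step 4: effect on the worst-score rule.** Take two visits before an intercurrent event.

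- Visit A (Q2 = 4, Q4 = 36, Q5 = 2): printed 10 + 0.9 × 0.2 = 10.18; corrected 28.
- Visit B (Q2 = 0, Q4 = 40, Q5 = 8): printed 0.8; corrected 80.

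The printed formula carries A forward as the worst visit; the corrected one carries B.

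**Step 5: could the brackets be read differently?** The printed expression has five opening and five closing round brackets and one square pair. It is balanced, and no bracket after the 100 encloses both terms.

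**The case against.** There are three fair points on the other side.

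First, the table row is split over two lines in the text available for review, so a lost outer pair of brackets cannot be fully excluded. This has little force. Both halves of the formula survive and the brackets balance, so a reading fault would have had to drop a matched pair without trace. Checking the SAP itself settles it.

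Second, the harm is conditional on the program following the printed string. The SAP defers detail to a Programming Specifications document that is not part of the material reviewed. A careful programmer has several cues to the right scale: the stated 0–100 range, the (%) label, the neighbouring rows, and the rule for those who worked no hours. That stands as a reason to check the program before assuming it is wrong. It does not rescue the SAP text, which is the only derivation given in either document. For SF-36 the SAP names certified scoring software; for WPAI-GH it names no such safeguard.

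Third, the consequence is small. WPAI-GH has no model, p-value or place in the testing hierarchy, and the two components of the overall score are each reported correctly on their own. The worst-score example is constructed, its frequency cannot be derived from the documents, and it follows from the same scaling slip and is not a second defect. All of this stands, and it limits the weight of the point.

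**Conclusion.** The concern holds. As printed, the formula adds a percentage to a fraction and contradicts the scale stated in the same section; nothing else in the protocol or SAP corrects it. At-work impairment contributes at most 1 point, and full impairment does not map to 100 for anyone who worked. These bounds follow from the algebra and from Q5 being a 0–10 scale, and hold for any working hours.

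The reach is narrow: one of four WPAI-GH scores, in an 'other' endpoint planned for descriptive summary only. It is worth correcting because a wrong value could pass into a published table, not because it threatens any conclusion of the trial. The assumption is that the printed bracket structure matches the source document. Whether the derivation program carries the error cannot be seen from these documents.

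**What to change.** In SAP section 4.4.1, replace the overall work impairment formula with

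100 × { Q2/(Q2+Q4) + [1 − Q2/(Q2+Q4)] × (Q5/10) }.

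Keep the existing rule for participants who missed work and worked no hours. Compare the programming specification and derivation code with the corrected formula and change them if they follow the printed one. A simple validation case is Q2 = 0, Q4 = 40, Q5 = 10, which must return 100.

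The cost is one formula in the SAP and, if the program carries the error, one line of code. The score is recomputed from Q2, Q4 and Q5, so no data collection changes.

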### 4.4.2. Main analytical approach

Summary statistics by visit will be provided for the SF-36 and WPAI-GH endpoints.

Summary of responder status by visit will be provided for the 28-point SNOT-22 responder endpoint.

Summary statistics for change from baseline at the key time-periods when it was collected will be provided for overall VAS score.

The change from baseline endpoints related to VAS and VRS scores will be analysed in the same way as the co-primary endpoints.

For the endpoint, achieving a meaningful decrease from baseline in their mean individual symptoms VRS and composite VRS from Week 49 through to Week 52 without first having nasal surgery (actual) or disease-modulating medication for CRSwNP, the clinically meaningful VRS cut-points for mean individual symptoms VRS and composite VRS are as follows:

- Achieving a 1-point or greater decrease from baseline in nasal obstruction VRS total score at Week 52 without first having nasal surgery (actual) or disease-modulating medication for CRSwNP
- Achieving a 1-point or greater decrease from baseline in rhinorrhoea VRS total score at Week 52 without first having nasal surgery (actual) or disease-modulating medication for CRSwNP
- Achieving a 0.9-point or greater decrease from baseline in loss of smell VRS total score at Week 52 without first having nasal surgery (actual) or disease-modulating medication for CRSwNP
- Achieving a 0.8-point or greater decrease from baseline in facial pain VRS total score at Week 52 without first having nasal surgery (actual) or disease-modulating medication for CRSwNP
- Achieving a 1-point or greater decrease from baseline in mucous in throat VRS total score at Week 52 without first having nasal surgery (actual) or disease-modulating medication for CRSwNP
- Achieving a 0.8-point or greater decrease from baseline in composite nasal polyps symptoms VRS total score at Week 52 without first having nasal surgery (actual) or disease-modulating medication for CRSwNP

• Achieving a 0.8-point or greater decrease from baseline in composite CRS symptoms and facial pain VRS total score at Week 52 without first having nasal surgery (actual) or disease-modulating medication for CRSwNP

The remaining other endpoints will be analysed as described below:

### **Endpoints**

- Achieving a one point or greater decrease from baseline in NP Score at Week 52 without first having nasal surgery (actual) or disease-modulating medication for CRSwNP.
- Achieving a meaningful decrease from baseline in their mean individual symptoms VRS and composite VRS from Week 49 through to Week 52 without first having nasal surgery (actual) or disease-modulating medication for CRSwNP.
- Achieving an 8.9 point or greater decrease from baseline in SNOT-22 total score at Week 52 without first having nasal surgery (actual) or disease-modulating medication for CRSwNP.

### **Model Specification**

The conditional treatment effect for the responder analysis endpoints will be estimated using
a generalized linear mixed model with a logit link function and covariates of treatment group,
baseline score, log(e) baseline blood eosinophil count, region, previous surgery for nasal
polyps, visit and interaction terms for visit by baseline score and visit by treatment.

### **Model Checking & Diagnostics**

 Pearson residuals will be plotted by using PLOTS=PEARSONPANEL option for the model statement in SAS.

#### **Model Results Presentation**

- For each scheduled visit / time-period the following will be presented:
  - The number and percentage of responders and non-responders for each treatment, together with the odds ratio, 95% CI and p-value will be presented for the NP responder endpoint, and nasal obstruction, loss of smell, and rhinorrhoea VRS responder endpoints only
  - Other individual symptom VRS and composite VRS responder endpoints (facial pain, mucous in throat, composite nasal polyps symptoms, composite CRS symptoms and facial pain) will be summarized only

# 4.5. Safety Analyses

The safety analyses will be based on the Safety Analysis Set, unless otherwise specified.

#### 4.5.1. Extent of Exposure

Two doses of study treatment will be administered during study treatment period: the first at randomisation Visit 2 (Week 0) and the second at Visit 10 (Week 26). Each dose is viewed as providing therapeutic coverage for 26 weeks (182 days). The number of treatments administered, and the number of days exposure will be summarised descriptively and listed. Total subject-year exposure will also be presented.

Number of days of exposure to study treatment will be calculated as follow:

Duration of Exposure in Days = (Date of Final Dose) - (Date of First Dose) + 182 days (regardless of study withdrawal or death)

Subject years exposure is calculated as follow:

Subject Years Exposure = ((Date of Final Dose) – (Date of First Dose) + 182)/365.25

